As treatment options may change over time, potential comparators will be assessed on a regular basis and if possible, a concurrent comparator group of IV zanamivir unexposed pregnant women with complicated influenza will also be recruited into the registry.

Background Prevalence Estimates of Pregnancy Outcomes

Background prevalence estimates of pregnancy outcomes in the general population, such as premature birth and LBW, are readily available from national vital statistics or publications in the scientific literature [Office for National Statistics, 2015]. Rates for a range of countries participating in the registry will be reviewed so that variation in background rates can be considered.

Background Prevalence Estimates of Major Congenital Malformations (MCMs)

Published prevalence estimates of MCMs are available from the European Registry of Congenital Malformation and Twin Registries (EUROCAT) which is an ongoing population-based birth defects surveillance program across Europe [EUROCAT, 2017]. EUROCAT is a European network of population-based registries covering 29% of the European population. It started in 1979 and covers 1.5 million births per year in Europe. Its primary objectives are to provide essential epidemiological information on congenital

malformations and to act as an information and resource centre to individuals and public health professionals.

As EUROCAT is primarily a passive surveillance system, background prevalence estimates from active surveillance approaches will also be considered. The Centre for Disease Control and Prevention's (CDC) Metropolitan Atlanta Congenital Defects Program (MACDP) actively searches for congenital malformations among the 50,000 annual births to residents of metropolitan Atlanta's 5 counties and abstracts medical records at all Atlanta obstetric hospitals, paediatric referral hospitals, genetics laboratories, and vital records [Correa-Villasenor, 2003]. MACDP data have been used as the comparator cohort in examinations of congenital malformations for other pregnancy registries despite differences in geographic focus (for example with other GlaxoSmithKline products including acyclovir, sumatriptan, lamotrigine, and zidovudine) [Honein, 1999]. The most recent CDC MACDP 5-year major malformation prevalence was 2.78% (6,945 cases with birth defects/249,999 live births) from 1999 to 2003.

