8.3.2. Outcome definitions

There are three groups of outcomes of interest:

Maternal outcomes

• Maternal death during pregnancy and up to 42 days after delivery.

Pregnancy outcomes

- Live birth defined as an infant born alive.
- Spontaneous abortion (SAB) in clinically recognized pregnancies defined as foetal death or expulsion of products of conception prior to 20 weeks' gestation, or if gestational age is unknown, weighing less than 500g.
- Stillbirths defined as a foetal death occurring at 20 weeks' gestation or greater, or if gestational age is unknown, a foetus weighing 500 g or more.
- IAB defined as voluntary interruption of pregnancy, including pregnancy termination that occurs electively, to preserve maternal health, or due to foetal abnormalities.

Birth outcomes

- Prematurity defined as an infant born at gestational age <37 weeks.
- SGA defined as an infant born with a birth weight less than the 10th centile for the corresponding gestational age.
- LBW defined as an infant whose birth weight is <2500 g.
- Neonatal death defined as death of the infant within 28 days of birth.
- Major congenital malformation (MCM) defined according to EUROCAT criteria
- EUROCAT includes all major structural malformations and chromosomal malformations. Minor anomalies are excluded (as defined in Section 3.2 of the coding guide) and cases with more than one malformation type are only counted once for the calculation of overall malformation prevalence.

Maternal and infant follow up is proposed to 3 months after birth. Longer term follow-up is not proposed as there are no pre-clinical or clinical data to suggest a signal for developmental delay. Hence, it is impossible to determine an appropriate longer term follow up period which differs substantially according to the type of developmental adverse outcome of interest. As the majority of major malformations are detected at birth, a three month follow up period is deemed adequate to maximize capture of major malformations.

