8.4. Data sources

The current UKOSS/INOSS reporters will serve as data reporters identifying exposures for the registry within the UKOSS and INOSS networks. The registry is strictly observational; the schedule of health care visits and encounters as well as all treatment regimens will be determined by the treating HCP. There will be no additional laboratory tests or assessments required as part of this registry. Only data noted as part of routine care will be collected. Maternal characteristics and outcome data will be provided by research staff, where accessible. To aid follow up, the mother will be asked to consent to medical record release and further contact to facilitate pregnancy and infant follow up.

Additionally, the teratologist/geneticist on the scientific advisory committee (SAC) will provide an opinion regarding the possible temporal association of the IV zanamivir

exposure to the development of any observed congenital malformations. If additional information is needed to aid in classification or temporality assessment, the teratologist will request additional information using a targeted follow up process. The SAC will meet periodically to review the data including a discussion of the MCM cases and their classification and temporality with the teratologist and to reach a consensus on the coding and classification of MCMs and other primary endpoints. Healthcare providers may also report de-identified data to the registry. This could include exposures and outcomes identified through anonymised healthcare electronic medical record data sources.

A summary of data that will be collected at specific time points and the source of data are provided in Section 8.6.2.1.

For critical data points, if there are outstanding questions, discrepancies between forms, or missing data, the appropriate reporter will be contacted for clarification. Up to three subsequent attempts, as necessary, will be made at regular intervals (e.g. every two weeks).

Exposure operational definition

At least one dose of IV zanamivir administered at any time during pregnancy will constitute exposure. If the anti-influenza medication to which the woman was exposed cannot be ascertained, an unknown exposure cohort will be established and -analysed separately. Given the short half-life of IV zanamivir (two hours) the start of the exposure window will be conception estimated as described below.

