8.5. Study size

The effect sizes that are expected to be detectable were calculated. The effect size is defined as the ratio of the prevalence in exposed patients, estimated from the study, to the prevalence in the reference population. These calculations were performed using a binomial distribution, a power of 80% and a 1-sided Type 1 (false positive) error rate of 5% [Altman, 1991]. Assuming prevalence values in the reference population of 2% (MCMs) and 7.6% (preterm births), 100 exposed live births will be sufficient to detect a 4-fold increase in the risk of MCMs and a 2-fold increase in the risk of pre-term birth, relative to the reference-population prevalence. The calculations were performed using the software PASS (Version 12.0.2, copyright 1983-2013, NCSS, LCC).

Table 1Detectable effect size assuming 80% power

Sample size of live births (N)	PTB reference 7.6% ¹	LBW reference 7.0% ¹	MCM reference 2.00% ²
5	6.45	7.00	24.51
20	4.12	3.69	10.10
50	2.61	2.83	5.38
100	2.05	2.07	3.90
150	1.85	1.91	2.99

Abbreviations: LBW = low birth weight; MCM = major congenital malformations; PTB = preterm birth. ¹Prevalence from Office for National Statistics, 2015 ²Prevalence from EUROCAT, 2017

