As EUROCAT includes chromosomal malformations and MACDP excludes chromosomal malformations, all malformations types will be collected through the registry and the appropriate comparisons will be made with and without chromosomal malformations. There will also be alignment of denominators around inclusion of foetal losses to ensure appropriate comparisons are being made between external reference groups and the registry. Pregnancies exposed to major teratogens (see Section 8.3.3) will be excluded from analyses.

If it is feasible, descriptive comparisons between the registry and an appropriate internal and/or external comparison group will be examined (see Section 8.2 for a description of potential reference groups).

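### Malformations are ascertained to 3 months after birth, but the planned comparison with EUROCAT and MACDP is not aligned on age at diagnosis, so it could lean towards no signal if those programmes count later diagnoses

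*Protocol*

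**What the plan says.** Section 8.3.2 sets the window: "Maternal and infant follow up is proposed to 3 months after birth". Its reason is that most major malformations are detected at birth, from which it concludes that "a three month follow up period is deemed adequate to maximize capture of major malformations". It gives no proportion. Section 8.4 adds that "Only data noted as part of routine care will be collected".

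Section 8.7.1 compares MCM prevalence with EUROCAT and MACDP. Under section 8.2 these are the primary population comparators when no suitable influenza-based comparator exists. Section 8.2 calls EUROCAT mainly passive surveillance. It describes MACDP as an active search that "abstracts medical records at all Atlanta obstetric hospitals, paediatric referral hospitals, genetics laboratories, and vital records". It gives no upper age at diagnosis for either programme.

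Section 8.7.1 plans two alignments. Comparisons will be made with and without chromosomal malformations, and "There will also be alignment of denominators around inclusion of foetal losses to ensure appropriate comparisons are being made". Age at diagnosis is not mentioned.

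Two upward influences on the MCM estimate are named: the choice to count only foetal losses with an MCM in the denominator (8.7.1), and enrolment after prenatal testing (8.9). Section 8.9 does not mention possible under-capture after 3 months.

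Section 8.5 states that "100 exposed live births will be sufficient to detect a 4-fold increase in the risk of MCMs", with a 2% reference prevalence.

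**The concern.** The protocol's own reason for the window concedes that some malformations are found after birth, and it does not show that nearly all of them are found by 3 months. The registry's numerator is cut at that age. If the reference numerators are not, the registry and its comparators count different things, and the ratio is pulled down whatever the drug does. For a registry meant to detect an increase in risk, that is the less safe direction of error.

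The gap lies within what the protocol chose to fix. It declares the window adequate, names the comparators and lists the features on which the comparison will be aligned. Section 8.5 also treats the registry as capturing malformations as completely as the reference, because one prevalence scale is used for both.

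**Working it through.** **Inputs.** From section 8.5: exact binomial against a fixed reference, "a power of 80% and a 1-sided Type 1 (false positive) error rate of 5" per cent, reference MCM prevalence p0 = 2%, and n = 100 or 150 live births. From section 8.2: MACDP prevalence 6,945/249,999 = 2.78%. Not in the protocol: the share f of reference-counted malformations that a 3-month window would miss. I take f = 10%, 20% and 30% as assumptions, with f = 0 as the protocol's implicit case.

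**Step 1: reproduce Table 1.** Find the smallest count r with P(X ≥ r | n, p0) ≤ 0.05, then solve P(X ≥ r | n, p1) = 0.80. The detectable ratio is p1/p0.
- n = 100, p0 = 2%: r = 5 gives 0.0508, which is too large; r = 6 gives 0.0155. Then p1 = 7.79% and p1/p0 = 3.90, as in Table 1.
- n = 150, p0 = 2%: r = 7 (0.0320), p1 = 5.99%, ratio 2.99, as in Table 1.

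All 15 cells of Table 1 reproduce to two decimals.

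**Step 2: allow for under-capture.** The registry then sees p = (1 − f) × RR × p0, while the reference stays at p0. With RR = 4 and p0 = 2%, p is 8.0%, 7.2%, 6.4% and 5.6% at f = 0, 10%, 20% and 30%. With p0 = 2.78%, p is 11.12%, 10.01%, 8.90% and 7.78%. Power is P(X ≥ r | n, p).

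Power for a true 4-fold increase:

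| Setting | r | f = 0 | f = 10% | f = 20% | f = 30% |
|---|---|---|---|---|---|
| n = 100, 2% | 6 | 82% | 73% | 62% | 49% |
| n = 150, 2% | 7 | 96% | 92% | 85% | 74% |
| n = 100, 2.78% (MACDP) | 7 | 94% | 88% | 80% | 67% |

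**Step 3: true ratio detectable with 80% power**, p1 / [p0 × (1 − f)], computed from unrounded p1:
- n = 100, 2%: 3.90, 4.33, 4.87, 5.57
- n = 150, 2%: 2.99, 3.33, 3.74, 4.28
- n = 100, 2.78%: 3.21, 3.57, 4.02, 4.59

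**Step 4: how much reserve there is.** At n = 100 and 2%, f = 5% already gives 78% for a 4-fold increase. At n = 150 and 2%, power stays at 80% up to about f = 25%. Against 2.78% at n = 100 it is 79.6% at f = 20%.

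**Step 5: the upward influences.** Leaving k foetal losses without an MCM out of a denominator of about 100 raises the estimate by a factor of about (100 + k)/100, or roughly k%. Section 8.7.1 already plans to align denominators. The effect of enrolment after prenatal testing cannot be quantified from the protocol; section 8.9 plans to examine the data with and without those cases. The net bias therefore cannot be computed.

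**The case against.** A reader might infer that the reference figures certainly include diagnoses beyond 3 months and that the registry therefore reads low. The protocol does not support that. It states no age limit for either programme. MACDP's use of paediatric referral hospitals and genetics laboratories suggests later diagnoses may be counted, but newborns are seen there too. For EUROCAT nothing bears on age. Reading low would also be a net statement, and the two named influences run the other way. This part of the objection stands, so the point is conditional.

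A reader might also infer that the registry searches less actively than its references. That fails for EUROCAT, which section 8.2 calls primarily passive. The registry follows each pregnancy individually, queries missing data with up to three further attempts, and lets a teratologist request more information (8.4). Relying on routine care means no added tests; it does not by itself mean passive case finding.

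Nor does section 8.7.1 present the whole MCM estimate as an over-estimate. Its remark on over-estimation concerns the denominator alone.

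On size, the setting of 100 live births and 2% is the least favourable of the three shown. The protocol proposes 100 to 150 exposures. The registry is descriptive, uses several comparators, and has its MCM cases reviewed by the advisory committee. Power thus measures the claim in section 8.5, not a formal decision rule. This limits the consequence.

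Finally, such detail could be left to the statistical analysis plan. But the protocol itself lists the alignment features, and age at diagnosis belongs in that list.

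**Conclusion.** The point holds in conditional form. The window, the comparators and the missing alignment on age at diagnosis are all on the page. The direction follows if, and only if, the comparators count diagnoses made after 3 months; the upward influences may then offset it partly or wholly.

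The size depends on the assumed late-diagnosed share. With 10% to 30% missed, power for a 4-fold increase loses about 9 to 33 percentage points at 100 live births and a 2% reference, 4 to 22 points at 150, and 5 to 27 points at 100 against 2.78%. The exposed spot is the statement that 100 live births suffice for a 4-fold increase: its 82% power leaves almost no reserve. Table 1 is not in error, and nothing here shows that a 3-month window is wrong in itself.

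**What to change.** In section 8.7.1, add age at diagnosis to the features on which registry and reference are aligned, and state the age up to which each comparator ascertains cases. Where the source allows it, use reference malformations diagnosed prenatally or by 3 months of age. Where it does not, report the ratio over a stated range for the late-diagnosed share. In section 8.9, add possible under-capture after 3 months as a limitation, with its direction.

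The cost is protocol wording and a request for, or tabulation of, reference data by age at diagnosis. The drawbacks are that restricted figures may exist for only some sources, and that a restricted reference rate will be lower. No longer infant follow-up is needed.

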8.3.3. Confounders and effect modifiers

Additional data will be collected as follows:

Maternal characteristics: Age, ethnicity, country.

Prenatal data: Last menstrual period (LMP), EDD, corrected estimated date of delivery (CEDD).

Prenatal tests: Name of test, date of test, result.

Obstetrical history: Previous pregnancies: live births, stillbirths, SABs, IABs, births with MCMs and family history of MCMs.

Pregnancy complications including preterm labour, pre-eclampsia and placental abruption.

Concurrent medical conditions influenza: including details of influenza episode such as length of hospital stay, HDU/ICU stay (and length of stay), supplemental oxygen, associated complications of influenza (including bacterial pneumonia, sepsis, myocarditis, encephalitis, acute respiratory distress, respiratory failure, bronchitis).

Concurrent medical conditions other: with emphasis on diabetes, hypertension, asthma and autoimmune conditions.

Concomitant medications and vaccines: Medications of specific interest will include teratogens based on the old FDA classification of medications labelled as category X. Lists of medications associated with teratogenicity will be taken from Briggs, 2009 which is consistent with the list used by the clinical geneticist of the North American Anti-Epileptic Drug Register [Holmes, 2004; Correa-Villasenor, 2003;. Medications will then be classified into strong teratogens (e.g., isotretinoin, thalidomide) and more modest teratogens (e.g., carbamazepine).

Tobacco use

Infant gender and multiple gestations

8.4. Data sources

The current UKOSS/INOSS reporters will serve as data reporters identifying exposures for the registry within the UKOSS and INOSS networks. The registry is strictly observational; the schedule of health care visits and encounters as well as all treatment regimens will be determined by the treating HCP. There will be no additional laboratory tests or assessments required as part of this registry. Only data noted as part of routine care will be collected. Maternal characteristics and outcome data will be provided by research staff, where accessible. To aid follow up, the mother will be asked to consent to medical record release and further contact to facilitate pregnancy and infant follow up.

Additionally, the teratologist/geneticist on the scientific advisory committee (SAC) will provide an opinion regarding the possible temporal association of the IV zanamivir

exposure to the development of any observed congenital malformations. If additional information is needed to aid in classification or temporality assessment, the teratologist will request additional information using a targeted follow up process. The SAC will meet periodically to review the data including a discussion of the MCM cases and their classification and temporality with the teratologist and to reach a consensus on the coding and classification of MCMs and other primary endpoints. Healthcare providers may also report de-identified data to the registry. This could include exposures and outcomes identified through anonymised healthcare electronic medical record data sources.

A summary of data that will be collected at specific time points and the source of data are provided in Section 8.6.2.1.

For critical data points, if there are outstanding questions, discrepancies between forms, or missing data, the appropriate reporter will be contacted for clarification. Up to three subsequent attempts, as necessary, will be made at regular intervals (e.g. every two weeks).

Exposure operational definition

At least one dose of IV zanamivir administered at any time during pregnancy will constitute exposure. If the anti-influenza medication to which the woman was exposed cannot be ascertained, an unknown exposure cohort will be established and -analysed separately. Given the short half-life of IV zanamivir (two hours) the start of the exposure window will be conception estimated as described below.

IV zanamivir exposure will be further categorized by earliest trimester of exposure. For this registry, gestational weeks will be estimated from the most reliable EDD as reported by the HCP. If a CEDD is provided by the HCP, it will be used instead. The date of conception will be calculated as the most reliable EDD/CEDD minus 38 weeks. If the EDD is not available or never estimated, the first day of the LMP may be used to estimate gestational age. The second trimester will be considered to begin at week 14 after the date of conception or LMP, and the beginning of the third trimester, at week 28. If there is a discrepancy between gestational age calculated from LMP and reported gestational age, the HCP will be asked to verify the data.

If HCPs provide de-identified data to the registry, they must be able to verify the date of exposure to IV zanamivir. Such data may come from data collected both within and outside of the UKOSS/INOSS network. For example, UKOSS has ethical approval to collect a minimum exposure and outcome dataset on women exposed to new influenza treatments (including IV zanamivir) with a waiver of informed consent. This will enable capture of some data on women who may be exposed to IV zanamivir during hospitalisation with complicated influenza, but do not consent to participate in this study with more complete data collection. A similar situation may arise with other INOSS centres. Other potential de-identified data sources include anonymised healthcare data sources.

Outcome operational definition

All outcome variables will be provided by research staff at sites. They will be asked to describe any MCMs observed in the infant or foetus and will also be asked to report the

gestational age and birth weight. These two variables will be used to calculate preterm birth, LBW, and SGA. Data will be abstracted from medical records. As described above a teratologist/ geneticist will review all reported congenital anomalies and classify them using the EUROCAT system [EUROCAT, 2017].

Operational variable(s) definition

The study staff will provide prenatal data (LMP, EDD, and CEDD), prenatal test data (test, date of test, and result), obstetrical history (previous pregnancies, live births, stillbirths, SABs, IABs, births with MCMs, and family history of MCMs), concurrent medical conditions, concomitant teratogenic medications, and tobacco use during pregnancy through the UKOSS/INOSS system. At pregnancy outcome, research staff will provide pregnancy outcomes data (live birth, stillbirth, SAB, IAB) and infant outcome (gestational age, birth weight, congenital malformations, gender and multiple gestation).

De-identified healthcare data:

If HCPs provide de-identified data to the registry, they will provide required data on maternal characteristics, prenatal data, obstetrical data, and pregnancy outcome data. De-identified data sources may include de-identified data collected under waiver of consent through the UKOSS/INOSS system or de-identified/anonymised healthcare electronic medical record sources where it is possible to identify this exposures and outcomes information.

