The prevalence of preterm births, SGA and LBW will be calculated as proportions, with the number of live births as the denominator. Because MCMs are often associated with preterm birth and LBW, sensitivity analyses will be performed excluding infants with MCMs from the numerator and denominator when prevalence estimates are determined for these outcomes.

Formulas for the calculation of prevalence of the primary outcomes are presented below:

Preterm birth prevalence =	Number of preterm live births Number of live births
SGA prevalence =	Number of SGA live births Number of live births
LBW prevalence =	Number of LBW live births Number of live births
MCM prevalence =	Number of live births and foetal losses occurring at ≥ 20 weeks gestation with MCM Number of live births (all) plus number of foetal losses with MCM

Due to inconsistent ascertainment of malformations in early foetal losses these are not included in analyses. Furthermore, a conservative approach is taken to only include foetal losses ≥ 20 weeks with MCMs, rather than all foetal losses, in the denominator. This will result in an over-estimation of risk.

Because most structural defects have their origins in the first trimester of pregnancy during the period of organogenesis, analyses of MCMs will be stratified by trimester of exposure, if applicable. The second trimester will start at 14 weeks gestation and the third trimester will start at 28 weeks gestation. The prevalence of combined MCMs reported to the registry will be calculated as a proportion with the number of MCMs in live births and foetal losses as the numerator and the number of all live births plus foetal losses with a MCM as the denominator. Pregnancy losses with reported MCMs occurring at or after 20 weeks' gestation will be included in the numerator of the estimate of risk for MCMs to increase sensitivity. The prevalence of combined MCMs in exposed cases will be compared with that reported to EUROCAT AND MACDP. Only cases meeting the EUROCAT criteria will be included in the primary analysis.

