8.9.1. Study closure/uninterpretability of results

The prevalence of exposure to IV zanamivir is likely to vary across influenza seasons influenced by factors such as the underlying pathogenicity and resistance profiles of circulating virus strains. Accordingly, an update report will be filed with the EMA each year, providing details of the number of treated patients enrolled and guidance on the likely study end date. This will be used to inform on a more realistic study end date. At present 100-150 IV zanamivir exposures are proposed to be sufficient to detect a 2-4-fold

increase in pregnancy outcomes of interest therefore detecting a signal of substantial increase in risk.

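### Section 8.4 joins malformation classification to the judgement of exposure timing, with no order or masking stated, so timing can influence borderline MCM cases

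*Protocol*

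**What the plan says.** Protocol section 8.4 (Data sources) describes the review of malformations. The SAC's teratologist/geneticist "will provide an opinion regarding the possible temporal association of the IV zanamivir" exposure to any malformation observed. Under the outcome operational definition in the same section, a teratologist/geneticist, introduced by a reference back to that description, reviews every reported anomaly and classifies it under EUROCAT. Section 8.6.1 repeats that this specialist reviews all classifications. The SAC's periodic meetings take the cases up in this way: "discussion of the MCM cases and their classification and temporality with the teratologist and to reach a consensus on the coding and classification". The same consensus extends to the registry's other main endpoints. A single targeted follow-up process supplies extra information for either judgement.

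Section 8.7.1 makes the classification decisive for the numerator: "Only cases meeting the EUROCAT criteria will be included in the primary analysis". It also stratifies the MCM analyses by trimester of exposure, because most structural defects arise in the first trimester. The overall prevalence is compared with EUROCAT and MACDP.

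Section 8.3.2 limits discretion: an MCM is defined by EUROCAT criteria, and minor anomalies are excluded by reference to the coding guide.

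On size, section 8.5 states that "100 exposed live births will be sufficient to detect a 4-fold increase in the risk of MCMs", with a 2% reference, 80% power and a one-sided 5% error rate.

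**The concern.** Temporality cannot be judged without the exposure date. If classification is settled in the discussion that weighs temporality, whoever decides whether an anomaly is major may know when the woman was treated, and hence in which stratum a drug-related defect would be expected. A borderline anomaly could then be counted more readily after first-trimester exposure and less readily after late exposure.

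Two features make this worth attention. The MCM result will rest on very few cases. And the EUROCAT and MACDP comparator counts do not pass through this committee, so a shift in classification would not cancel in the comparison. The effect bears most on the trimester strata, where exposure timing is itself the stratifier.

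**Working it through.** **Step 1. Set the text side by side.**

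| Question | What the protocol gives |
|---|---|
| Who classifies? | The teratologist/geneticist (8.4, 8.6.1), then SAC consensus (8.4) |
| Who judges temporality? | The same role, discussed at the SAC (8.4) |
| In what order? | Not stated |
| Is exposure timing withheld at classification? | Not stated |
| Does temporality decide what counts? | Not stated; the only stated criterion is EUROCAT (8.7.1) |

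**Step 2. Reproduce Table 1.** Inputs from section 8.5: reference prevalence p0 = 0.02, one-sided alpha 0.05, power 0.80. Method: exact one-sample binomial. Find the smallest r with P(X ≥ r | n, p0) ≤ 0.05, solve P(X ≥ r | n, p1) = 0.80 for p1, and report p1/p0.

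| n | r | P(X ≥ r) at 2% | Ratio computed | Table 1 |
|---|---|---|---|---|
| 20 | 3 | 0.0071 | 10.10 | 10.10 |
| 100 | 6 | 0.0155 | 3.90 | 3.90 |
| 150 | 7 | 0.0320 | 2.99 | 2.99 |

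Table 1 therefore implies a cut-off of 6 cases in 100. The protocol does not state this as a decision rule.

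**Step 3. Read the same cut-off from the one-sided interval in section 8.7.1.** The exact lower 95% limit for x cases in n is the 0.05 quantile of Beta(x, n − x + 1). For n = 100:

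- 5 cases: 1.99%, just below 2%; P(X ≥ 5 | 2%) = 0.0508.
- 6 cases: 2.64%, above 2%; P(X ≥ 6 | 2%) = 0.0155.

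Against the MACDP figure quoted in section 8.2 (2.78%) the step falls between 6 cases (P = 0.061, limit 2.64%) and 7 (P = 0.022, limit 3.33%).

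**Step 4. Worst case for one misclassified case at n = 100.** The assumption is that exactly one case is shifted in every replicate.

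- Always one added: the effective cut-off is 5, and the false-signal probability goes from 0.0155 to 0.0508.
- Always one lost: the effective cut-off is 7, and power at 3.90-fold (p = 0.078) goes from P(X ≥ 6) = 0.801 to P(X ≥ 7) = 0.671.

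At n = 150, the upper end of the planned exposures in section 8.9.1, and counting all 150 as live births, the same shifts take the false-signal probability from 0.032 to 0.082, and power at 2.99-fold from 0.80 to 0.68.

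**Step 5. How often one case could matter at n = 100.** One added case crosses the cut-off only from a count of 5; one lost case crosses it only from 6.

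| True prevalence | P(X = 5) | P(X = 6) | Sum |
|---|---|---|---|
| 2% | 0.035 | 0.011 | 0.047 |
| 4% | 0.160 | 0.105 | 0.265 |
| 7.8% | 0.097 | 0.130 | 0.227 |

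If one case were up-classified in only 10% of studies (an assumption, taken as independent of the count), the false-signal probability would be 0.0155 + 0.10 × (0.0508 − 0.0155) = 0.019.

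**Step 6. A small stratum.** The protocol gives no first-trimester number. Taking n = 20 purely as an illustration, the cut-off is 3. One case always added takes 0.0071 to 0.0599, and one always lost takes power at 10.10-fold from 0.80 to 0.60.

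**The case against.** The strongest reply is that the protocol nowhere says the two judgements are made in one step. Section 8.4 lists topics for SAC meetings and sets no order, and its outcome definition and section 8.6.1 describe classification without mentioning exposure timing. A reader might infer that major or not is always decided with the exposure date known. That is a plausible reading of a joint discussion, but not a stated rule.

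A reader might also infer that one case crosses the plan's signal threshold. The plan has none: sections 7, 8.7.1 and 8.7.3 call the registry descriptive. The cut-off of 6 is derived from Table 1, and one case matters only next to it. The 5.1% false-signal figure assumes a shifted case every time, and even then barely exceeds the 5% error rate that section 8.5 accepts; much of the rise uses up slack left by the discreteness of the binomial.

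Other points also carry weight. The EUROCAT exclusion of minor anomalies leaves less room for judgement, and the documents do not show how many anomalies would be borderline. Upward shifts for early exposure and downward shifts for late exposure would partly offset in the overall estimate. Section 8.7 expects most exposure after prenatal screening, so the early stratum may be small, but its size is unknown. Masked review could be set out in a committee charter; section 2.4 leaves the SAC's composition open.

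These points limit the size and certainty of the concern. They do not remove it: section 8.4 itself puts classification and temporality in one discussion, requires a consensus on classification, and offers no separation.

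**Conclusion.** The point holds as a cheap improvement to a stated procedure, not as an error in the numbers. Section 8.4 assigns both judgements to one role and has the SAC discuss them together before it agrees the classification, with no order or masking. Knowledge of exposure timing can therefore influence borderline cases, mainly in the trimester-stratified MCM estimates.

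The size is bounded. At 100 live births and a 2% reference, one case changes the reading only at a count of 5 or 6. Movements from 1.5% to 5.1% in false signals and from 80% to 67% in power are worst cases on a derived cut-off. The documents give no basis for estimating how often a borderline case would arise, and any first-trimester stratum size is an assumption.

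**What to change.** In section 8.4, state three things:

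1. The teratologist/geneticist and the SAC complete and lock the EUROCAT classification of every reported anomaly from a case summary that withholds exposure date, trimester, gestational age at exposure and dose.
2. Exposure timing is released, and temporality assessed, only afterwards.
3. The temporality opinion does not alter the MCM numerator.

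The cost is the small effort of preparing a two-part case summary; reviewers and cases stay the same. Sample size, the implied cut-off of 6 in 100 and power are unchanged. One limit remains: every woman in the main cohort is exposed, so only the timing and dose can be withheld, not exposure itself. The change therefore protects the trimester strata more than the overall comparison with EUROCAT and MACDP.
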